2.9.3 Age and weight dependency

PK parameters will be generated for all subjects over the whole duration of the study. Since the physiological changes in Type 1 SMA subjects is very dynamic, the PK parameters AUC (AUCinf after first administration, AUCtau or AUC0-168h after all other administrations), Cmax, CL/F, Vz/F, and T1/2 will be correlated with both age and weight. For Parts 1 & 3, AUC and Cmax will be dose-normalized using unit mg/kg. For Parts 2 & 3, the age and weight dependency will be executed for each dose independently. Scatter plots of PK parameters versus both age and weight at the time of the dose when PK parameter was calculated, including a regression analysis, will be provided on the individual level.

The analysis will be carried for each study part separately.

2.9.4 Comparison of dosing methods

Branaplam can be administered either *via* tube administration or orally. To test the impact of the dosing method on the systemic exposure, the exposure parameters AUC (AUCtau or AUC0-168h) and Cmax will be compared between both dosing methods. The comparison will be executed for each subject individually, who was treated with both methods. Since the number of oral administrations per subject is considered to be low, especially when compared to tube administration, proposed assessments might be not feasible for all subjects treated with both methods.

Two assessments will be executed (if feasible) for Parts 1 & 3:

- Exposure parameters across the complete study duration will be dose-normalized using unit mg/kg and summary statistics for each method executed. Box plot comparing the two dosing methods will be prepared for each PK parameter.
- Exposure parameters of two subsequent profiles, of which one was derived after tube administration and the other after oral administration, will be dose-normalized using unit mg/kg. The ratio will be calculated between tube administration and oral administration.

For Parts 2 & 3, the same will be executed (if feasible) but without dose-normalizing. Results will be computed and displayed for each dose individually.

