5.2 Treating the patient

5.2.1 Preparation and dispensation

Branaplam will be administered to the patient via the following route of administration:

Part 1:

• Enteral (via a feeding tube) during the initial treatment period of 13 weeks

• Either oral or enteral during the following extended treatment periods. The decision of the route of administration will be performed by the Investigator depending on the patient's ability to swallow.

Detailed information on how the transition from enteral to oral administration should be performed are given in the Site Operations Manual.

Part 2:

- Enteral (via a feeding tube) for the first administration on Day 1
- Either oral or enteral for the rest of the study. The decision of the route of administration will be performed by the Investigator depending on the patient's ability to swallow.

The option to administer branaplam orally may be reconsidered based on emerging PK data or if oral administration of the investigational drug is not tolerated by the patient following 2 consecutive attempts and as documented by the Acceptability and Palatability Questionnaire (see Table 7-3 and Section 7.5.1).

In Part 1 and Part 2 of the study branaplam may be administered at the study site, or at the patient's home by a qualified clinician or parent / legal guardian.

See the Site Operations Manual for further details. Sponsor qualified medical personnel will be readily available to advise on trial related medical questions or problems.

Part 3:

- Similarly to Part 1 and Part 2 of the study, in Part 3 branaplam can be administered by oral or enteral application. The decision of the route of administration will be performed by the Investigator depending on the patient's ability to swallow.
- Patient will receive first dose at Visit 1 and continue weekly drug administration at home administrated by parents/caregivers or qualified personnel.
- At all of the visits where PK is collected the study drug administration should be performed at the site.
- Dispensation and return of study drug is described in Site Operations Manual

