2.9.2 Accumulation ratio

Part 1

In subjects, who received the same dose in the first two treatment cycles of 3 months each, the parameters AUC0-168h for both observations and Cmax will be log transformed and used in an ANCOVA model with day as a factor, log dose as a covariate and day by dose interaction and subject as random effect. The LSMeans and their mean difference between treatment cycle 2 and Day 1 for each dose level, together with 90% confidence limit will be calculated from this model. These will be back-transformed to provide an estimate of the accumulation ratio with corresponding 90% CI.

Part 2

Accumulation ratio can be estimated as described for Part 1. Since no intra-individual dose escalation is planned, the accumulation will be estimated for each observation period versus first administration.

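### SAP 2.9.4 lets first-dose profiles into the tube/oral comparison, so in Part 2 route can be inseparable from dosing occasion

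*SAP*

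**What the plan says.** SAP 2.9.4 sets out to test whether the dosing method affects exposure, within children treated both ways: "the exposure parameters AUC (AUCtau or AUC0-168h) and Cmax will be compared between both dosing methods". Two assessments are planned where feasible:

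- Summaries and box plots by route over the whole study.
- A tube/oral ratio from two consecutive profiles, "of which one was derived after tube administration and the other after oral administration".

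Parts 1 & 3 use dose-normalised values. Parts 2 & 3 do the same by dose without normalising. The section does not mention first versus repeat dose, or age.

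Protocol 5.2.1 fixes the route at the start:

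- Part 1: "Enteral (via a feeding tube) during the initial treatment period of 13 weeks", then "Either oral or enteral during the following extended treatment periods".
- Part 2: "Enteral (via a feeding tube) for the first administration on Day 1", then either route according to ability to swallow. Part 2 inclusion criterion 6 (Protocol 4.1.2) ties the tube after the first dose to children who cannot be dosed orally.

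The SAP has two conventions for first-dose AUC. Section 2.9.3 uses "AUCinf after first administration, AUCtau or AUC0-168h after all other administrations". The Part 1 accumulation model in 2.9.2, to which Part 2 refers, says "the parameters AUC0-168h for both observations and Cmax will be log transformed", so Day 1 is included as AUC0-168h. Section 2.9.4 does not say which applies.

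**The concern.** A within-child route comparison is informative only if the two profiles differ in little besides route. In Part 2 the first profile is by tube by design, and any oral profile is a repeat dose in an older child. For some children no other pairing exists. Their tube/oral ratio then carries accumulation and any age trend along with route, and the data from those children cannot separate them.

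The same two profiles would also be reported twice under different names. For Part 2, SAP 2.9.2 compares each later observation period with the first administration and calls it accumulation. For a child oral from month 3, 2.9.4 inverts that contrast and calls it route. A reader of the study report could take a ratio below 1 as lower exposure by tube when it only reflects weekly dosing.

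**Working it through.** SAP 2.9.4 states no figure to reproduce. The check sets out which pairs are possible, then sizes the non-route part of the ratio from the protocol's own pharmacokinetics.

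**Possible pairs in Part 2.** Protocol 1.1.1 names the observation periods as first dose, month 3 and month 9, and Table 7-3 agrees (serial sampling from Days 1, 92 and 274). Part 3 yields only Ctrough and C4h (Protocol 7.5.1), so it adds no AUC profile.

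| Route at first dose / month 3 / month 9 | Adjacent tube/oral pair |
|---|---|
| tube / oral / oral | first dose vs month 3 only |
| tube / tube / oral | month 3 vs month 9 (both repeat-dose) |
| tube / oral / tube | first dose vs month 3, and month 3 vs month 9 |
| tube / tube / tube | none |

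The first row is where route and occasion coincide completely.

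**Possible pairs in Part 1.** The extension cycle (Table 7-2) starts with a profile at Day 92 and repeats, with either route allowed. A Day 1 tube profile could still be paired with a Day 92 oral one, but repeat-dose pairs by both routes are also available.

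**Half-life check.** T1/2 = ln2 × (Vz/F)/(CL/F), with the Part 2 values in Protocol 1.1.1:

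- 0.625 mg/kg: 0.693 × 40000/660 = 42.0 h (stated 42.2)
- 2.5 mg/kg: 0.693 × 52400/781 = 46.5 h (stated 46.0)

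The inputs are consistent.

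**Accumulation in AUC0-168h.** With linear kinetics and weekly dosing, repeat/first = 1/(1 − exp(−ln2 × 168/T1/2)). The tube/oral ratio for a first-dose tube profile against a repeat-dose oral one is the reciprocal, with no route effect:

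| T1/2 (h) | Source | Repeat/first | Tube/oral |
|---|---|---|---|
| 42.2 | Part 2, low dose | 1.068 | 0.94 |
| 46.0 | Part 2, high dose | 1.086 | 0.92 |
| 37.4 | Part 1, shortest | 1.047 | 0.96 |
| 59.3 | Part 1, longest | 1.163 | 0.86 |

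**Age drift.** Protocol 1.1.1 gives maximum increases of 1.2-fold (AUC) and 1.4-fold (Cmax) over 2.5 to 58.5 months, a span of 56 months. Assuming linearity, three months adds 0.2 × 3/56 = 1.1% for AUC and 0.4 × 3/56 = 2.1% for Cmax.

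**Combined, first-dose tube vs month-3 oral, Part 2.** AUC0-168h: 1.068 × 1.011 = 1.08 to 1.086 × 1.011 = 1.10. Cmax, if it accumulates by the same factor: 1.068 × 1.021 = 1.09 to 1.086 × 1.021 = 1.11.

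**Effect of the AUC convention.** With linear, stationary kinetics, AUCinf after a first dose equals AUC over the dosing interval at steady state. Using AUCinf for the first dose, as in 2.9.3, would remove the accumulation part from AUC. It would do nothing for Cmax.

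**How many profiles are repeat-dose.** Each child has at most one first-dose profile. Part 1 (Table 1-1): 11 + 4 + 6 + 16 + 52 = 89 Cmax profiles and 13 treated, so at least 76 (85%) are repeat-dose. Part 2 (Table 1-2): 29 + 38 = 67 and 25 treated, so at least 42 (63%). The split by route is not given, so the number of affected pairs cannot be computed.

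**The case against.** The strongest reply is that 2.9.4 sets no order and no first-dose condition. A reader might infer that pairing a first-dose tube profile with a later oral one is the rule of the comparison. The documents do not support that: Part 1 offers repeat-dose pairs, a Part 2 child on tube at month 3 and oral at month 9 gives one too, and the SAP itself expects few oral administrations relative to tube. This part of the reply stands.

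Second, 2.9.4 names only AUCtau or AUC0-168h, which 2.9.3 and the footnotes to Protocol Tables 1-1 and 1-2 assign to doses after the first. On that convention first-dose AUC is already out. But 2.9.2 uses AUC0-168h on Day 1, so the point is open, and no such restriction exists for Cmax.

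Third, the size is modest. The protocol saw no obvious accumulation in a Part 1 subset, and reported AUC CVs are about 22-29%. Those CVs mix between- and within-child variation, however, and a shift in one direction does not average out over pairs. A reader might quote the 1.2- and 1.4-fold age figures as the distortion. They span 56 months and do not describe adjacent profiles.

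Fourth, the study is non-confirmatory, the section is descriptive and conditional on feasibility, and accumulation and age dependency are reported separately. That limits the harm. It does not make the Part 2 ratio a route effect.

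**Conclusion.** The point holds in a limited form. SAP 2.9.4 does not say how first-administration profiles are treated. For Part 2 children who are oral from month 3 onward, the only available pair confounds route with occasion. If AUC0-168h is used for the first dose, the non-route shift from accumulation is about 7-9% in Part 2. In Part 1 the pooled box plots still include first-dose tube profiles, but repeat-dose pairs exist.

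This rests on linear kinetics, the reported mean half-lives, linear age drift and, for Cmax, the same accumulation factor as AUC. The direction of the age component is less certain: Part 1 showed a small increase with age, while Protocol 3.5.5 expected maturation to reduce exposure.

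A reader might also infer that the choice of route in Part 3 depends on this analysis. Protocol 5.2.1 bases that choice on ability to swallow, and the protocol's statement of no obvious route impact stands in its Part 1 results. The consequence is confined to how the Part 2 route ratio is read. This is a minor but worthwhile correction.

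**What to change.** In SAP 2.9.4, choose one of the following and state it:

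- Restrict both the pooled summaries and the adjacent pairs to repeat-dose profiles, for AUC and Cmax alike. This is the simpler option.
- If first-dose profiles are kept, use AUCinf for them as in 2.9.3. Model log exposure (dose-normalised for Parts 1 & 3) on route, first versus repeat occasion, and age, with a subject random effect. Route and age alone would not be enough, because the first/repeat term is what separates accumulation from route.

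In either case, add that if no Part 2 child has repeat-dose profiles by both routes, the Part 2 route effect is reported as not estimable.

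The cost is SAP wording and fewer usable pairs, possibly none in Part 2. No new data are needed.

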a: mean ± Standard Deviation (SD); b number of PK profiles considered; please note, that a patient provides several PK profiles to the analysis; c: AUC corresponds to the area under the plasma (or serum or blood) concentration-time curve from time zero to infinity [mass x time / volume] (AUCinf) after the first dose and the area under the plasma (or serum or blood) concentration-time curve from time zero, which is equal to the dosing time to 168 h [mass x time / volume] (0AUC0-168h) after multiple doses

Dose-normalized AUC and Cmax values across the age range from 2.5 to 58.5 months ranged from 595 to 2360 (h*ng/mL)/(mg/kg) and from 10.3 to 57.0 (ng/mL)/(mg/kg), respectively, and seemed to be comparable across the age range investigated. Linear regression analysis, which considered all dose-normalized exposure values, indicated a minor age-dependent increase with a maximum of 1.2 (AUC) and 1.4-fold (Cmax) increase across the observed age range. Similar assessment has been executed across the body weight range (5.11 kg to 16.3 kg). Comparable observations were made when dose-normalized AUC and Cmax values were correlated with the body weight range from 5.11 to 16.3 kg. Exposure values seemed to be comparable across the body weight range investigated. Linear regression analysis indicated a minor body weight-dependent increase of dose-normalized AUC and Cmax by 1.4 and 1.3-fold, respectively, considering the minimum and maximum observed body weight. No obvious impact of the administration method (feeding tube versus oral) was observed on both plasma exposure parameters, AUC and Cmax.

In Part 2 of present study, PK parameters were investigated across all observation periods at actual mean doses of 0.625 and 2.5 mg/kg, Table 1-2). Following oral branaplam administration across all observation periods, median Tmax values of branaplam in plasma ranged between 3.75 and 4 h at all observation periods (after 1 dosing, at month 3 and months 9). Thereafter, branaplam decreased slowly from plasma with mean apparent terminal elimination T1/2 values of 42.2 h and 46.0 h at the low and high dose level, respectively. AUC and Cmax values increased approximately with increasing dose in a dose-proportional manner. Mean apparent systemic clearance (CL/F) were 660 and 781 mL/h/kg and volume of distribution (Vz/F) values 40000 and 52400 mL/kg for 0.625 mg/kg and 2.5 mg/kg, respectively. Overall, all PK parameters were comparable to those observed in Part 1 (see above).

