2.9 Pharmacokinetic endpoints

[figure not shown]
Parts 1 & 3 and Parts 2 & 3

The following pharmacokinetic parameters will be analyzed: Cmax, Tmax, AUCtau or AUC0-168h, AUClast, AUCinf, T1/2, Vz/F and CL/F from the plasma concentration-time data.

Descriptive analyses

Branaplam plasma concentration data will be listed by study part, administered dose, subject, and sampling time point. Descriptive summary statistics will be provided by dose level (see [Table 1-2](#)) and sampling time point. Summary statistics will include mean (arithmetic and geometric), SD, CV (arithmetic and geometric), median, minimum, maximum, and the frequency (n, %) of concentrations below the LLOQ. Concentrations below LLOQ will be treated as zero in summary statistics and for PK parameter calculations. A geometric mean will not be reported if the dataset includes zero values. For all doses, the unit is transferred from “mg/m²” to “mg/kg” for summary statistics calculation. The summary statistics table also include columns with treatment group in Parts 2 & 3. A geometric mean will not be reported if

the dataset includes zero values. Graphical methods will be employed to show mean and individual concentration-time profiles. Pharmacokinetic parameters will be listed by study part, administered dose and subject and summarized by dose with descriptive summary statistics as described above. An exception to this is Tmax where median, minimum and maximum will be presented.

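### SAP 2.9.4 compares tube and oral exposure without a confidence interval, so with few paired children it cannot show which route differences are excluded

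*SAP*

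**What the plan says.** The aim in SAP 2.9.4 is to test whether giving the drug by tube or by mouth changes systemic exposure. The level of comparison is the child: "The comparison will be executed for each subject individually, who was treated with both methods". Two assessments are planned for Parts 1 & 3, both subject to feasibility.

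- Dose-normalised exposures over the whole study, with "summary statistics for each method executed" and a figure: "Box plot comparing the two dosing methods will be prepared for each PK parameter".
- Two successive profiles in a child, one by each route: "The ratio will be calculated between tube administration and oral administration".

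Parts 2 & 3 get the same treatment by dose, without normalising. The section itself expects few oral administrations per child. SAP 2.9 defines the statistics: "Summary statistics will include mean (arithmetic and geometric), SD, CV (arithmetic and geometric), median, minimum, maximum", plus the frequency of values below the LLOQ. An interval is not among them.

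SAP 2.9.2 handles the accumulation ratio differently. It fits a log-scale ANCOVA with subject as a random effect, and then: "These will be back-transformed to provide an estimate of the accumulation ratio with corresponding 90% CI".

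On the data so far, protocol 1.1.1 states for Part 1: "No obvious impact of the administration method (feeding tube versus oral) was observed on both plasma exposure parameters, AUC and Cmax". It gives no ratio, interval, number of children or method. Protocol 5.2.1 adds, under Part 2: "The option to administer branaplam orally may be reconsidered based on emerging PK data".

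**The concern.** Both routes are in use, and the reader of the final report will want to know whether exposure is similar by either. A point ratio near 1, or two overlapping boxes, says only that no difference stood out. It does not say how large a difference the data could have hidden, and that matters most when one route has few observations. The same SAP attaches a 90% CI to another within-child exposure ratio (accumulation) on the same parameters and gives no reason for doing less here. What is at stake is how a statement such as the one in protocol 1.1.1 is read: without an interval, it may be taken as evidence of similarity that the data may not contain.

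**Working it through.** **Plan's own figure.** There is none: no sample size, margin or precision is stated for the route comparison. The inputs can be checked, however. CV = SD/mean gives 1030/4280 = 24.1% (Table 1-1, AUC at 60 mg/m², printed 24.2) and 909/3470 = 26.2% (Table 1-2, AUC at 2.5 mg/kg, printed 26.2). The other AUC and Cmax cells also agree to within 0.1 point.

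**Inputs.**
- Total CV across profiles: AUC 22.3–28.5%, Cmax 22.8–40.5% (Tables 1-1 and 1-2). These are not within-child values.
- Within-child CV: not in the documents; assumed 15–35%. The 35% end exceeds every reported total CV for AUC, so it is relevant to Cmax only.
- Children with both routes: not in the documents; assumed 4 to 13 (13 were treated in Part 1).

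**Formulas.** Log-scale SD σ = √ln(1+CV²). SD of one child's log ratio = σ√2. 90% CI around an observed geometric mean ratio of 1.00 from n pairs = exp(± t₀.₉₅,ₙ₋₁ · σ · √(2/n)).

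**One child's ratio.** At CV 25%, σ = √ln(1.0625) = 0.246 and σ√2 = 0.348. With no route effect, 90% of single ratios lie in exp(±1.645 × 0.348) = 0.56–1.77. At CV 15% the range is 0.71–1.41, and at 35% it is 0.45–2.21.

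**Mean ratio over n pairs.** At CV 25% and n = 6: 2.015 × 0.246 × √(2/6) = 0.286, so the CI is 0.75–1.33. At n = 13: 1.782 × 0.246 × √(2/13) = 0.172, so the CI is 0.84–1.19.

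| Within-child CV | n = 4 | n = 6 | n = 13 |
|---|---|---|---|
| 15% | 0.78–1.28 | 0.84–1.19 | 0.90–1.11 |
| 25% | 0.66–1.51 | 0.75–1.33 | 0.84–1.19 |
| 35% | 0.57–1.76 | 0.67–1.49 | 0.79–1.27 |

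**Would a real difference show?** From the noncentral t at CV 25%, the chance that the 90% CI lies wholly below 1 is 39% (n = 6) or 70% (n = 13) for a true 20% loss. For a true 30% loss it is 69% or 97%.

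**All profiles pooled.** Table 1-1 holds 10+4+6+11+41 = 72 AUC and 11+4+6+16+52 = 89 Cmax profiles. If 10 of the 72 were oral (assumed, CV 25%), the 90% CI around 1 would be about 0.87–1.15. If 5 of the 89 were oral (CV 35%), it would be about 0.77–1.30. Both are optimistic, because repeat profiles from one child are treated as independent.

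**Age and order of routes.** Under protocol 5.2.1, Part 1 is tube-only for 13 weeks and Part 2 starts by tube, so oral profiles come later. Protocol 1.1.1 reports a rise of up to 1.2-fold (AUC) and 1.4-fold (Cmax) over ages 2.5 to 58.5 months. Over that full range, a true ratio of 0.80 could appear as 0.80 × 1.2 = 0.96 or 0.80 × 1.4 = 1.12. Between profiles 6 months apart the drift is small: 0.2 × 6/56 ≈ 2% and 0.4 × 6/56 ≈ 4%. It therefore threatens the pooled box plots far more than the successive-profile ratios.

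**The case against.** Route is not an objective or endpoint, all parts are declared non-confirmatory, and the section is conditional on feasibility, so a descriptive comparison is a defensible choice. The planned statistics include geometric means, from which a point ratio can be derived. Pairing successive profiles already limits age drift. These points stand. They keep the matter minor, but they do not supply an interval. SAP 2.9.1 is redacted, so an interval there cannot be excluded, but 2.9.4 does not refer to it.

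A reader might infer more than the documents support:

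- **That the protocol's Part 1 statement was produced by the SAP 2.9.4 method.** Protocol 1.1.1 gives no method, and SAP 2.9.4 plans the final analysis; nothing links them.
- **That a 20–30% exposure loss would go unnoticed.** This depends on two unknowns. It is plausible with few pairs, but at CV 25% with 13 pairs a 30% loss would nearly always show, and 10 oral profiles among 72 would probably reveal a loss of that size.
- **That the choice of oral dosing rests on this analysis.** Protocol 5.2.1 speaks of emerging PK data during conduct and does not mention 2.9.4.
- **That an equivalence margin is missing.** The plan never claims equivalence. As an illustration, placing the 90% CI inside 0.80–1.25 with 80% power (true ratio 1, CV 25%, simulated) would take about 23 pairs, more than the 13 children treated in Part 1.

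**Conclusion.** The concern holds as a reporting gap of low severity. SAP 2.9.4 promises a test of route and specifies no interval; protocol 1.1.1 reports on route with neither estimate nor interval. Under the central assumption (within-child CV 25%), even a ratio of exactly 1.00 leaves differences of roughly 25–33% open with 6 pairs and 16–19% with 13. These limits move with the two assumed quantities, from 0.90–1.11 (CV 15%, 13 pairs) to 0.57–1.76 (CV 35%, 4 pairs, Cmax only). The documents do not show that a route effect exists or that one has been missed.

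**What to change.** In SAP 2.9.4, add a mixed model on log AUC and log Cmax, following the approach of SAP 2.9.2. Exposures would be dose-normalised in Parts 1 & 3 and handled by dose in Parts 2 & 3, as now. Route is the fixed effect of interest, age or time since first dose a covariate, and subject a random effect. The covariate is needed because oral profiles come later; route and subject alone would put an interval around a ratio confounded with age.

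Report the oral/tube geometric mean ratio with its 90% CI and the numbers of children and profiles per route. Keep the box plots and per-child ratios as displays. Word any statement on route, including the one in protocol 1.1.1 when it is next updated, from that interval: which differences are excluded and which are not. No formal equivalence margin is required.

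The cost is one further model on data already collected. The drawback is that the interval may be wide, more so once age or time is adjusted for, and the comparison may read as inconclusive.
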